6.2 Safety Assessments

Tables and listings will be created for all TEAEs, defined as those occurring on or after first product use. However, the primary evaluation of safety will be the subpopulation of safety AEs that are urogenital, product-related, and/or serious. Data will be presented by presence of ZB-06 film according to relatedness of the finding to study product, whether AEs had onset before or after intercourse, and noted by gender, and the severity/seriousness of the AE.

In addition, concentrations of cytokines and chemokines will be described at baseline and after ZB-06 film use, as a surrogate of subclinical safety endpoints. Safety bloods (hematology, and metabolic panel) will be obtained at screening at Visit 8. Urinalysis will be done at the times indicated in the Schedule of Events (Appendix A)

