- The participant will be asked whether she refrained from intercourse and the use of intravaginal products and whether her male partner refrained from ejaculation during the previous 72 hours. If instructions were not followed, she will be reinstructed. If she used a spermicide or spermicidally lubricated condom during the previous 72 hours, the visit will be rescheduled in the next cycle. Otherwise, the visit may continue at the investigator's discretion.
- Urine will be obtained for urinalysis and reflex urine culture at visits 3 and 6.
- A urine pregnancy test will be performed at visit 6
- A blood sample (approximately 3 teaspoons) will be obtained at visits 6 and 9. The participant will undergo a pelvic exam during which a sample of cervical and vaginal secretions will be examined for midcycle characteristics and the presence of sperm. At visits 3 and 6, a colposcopy exam of the cervix and vagina will be done to determine if there are signs of irritation of the external genitalia, cervix, and vagina, as observed with the naked eye will be noted.
- Vaginal pH will be determined at visits 3 and 6. A slide for Nugent score will be obtained at visit 6
- A speculum exam will be performed and vaginal swabs, aspirate, endocervical mucus and a cervicovaginal fluid lavage (CVL) will be obtained.
- If sperm are found in the vagina or cervical mucus, the baseline cycle will be rescheduled for the following month and instructions on the use of condoms and avoidance of ejaculation will be reviewed. Longer abstinence may be recommended

for couples that have reportedly complied with the required 72-hour period. Additional supplies will be provided as needed.

- If the cervical mucus score is <10, the participant may be asked to return in 1 or 2 days if it seems likely that the midcycle point has not yet been reached, or in the next cycle if it seems likely that the midcycle point has already passed.
- If no sperm are detected at this visit, and the cervical mucus score is ≥10, the participant will be instructed to return home and have intercourse without a condom 2 to 3 hours prior to Visits 4, 7 or 10, which will be scheduled for the same or following day, within 27 hours of the mucus check visit.

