- At visit 6, we will provide the participant with a ZB-06 film to use and instruct her to insert the film deep in to the vagina about 30 minutes prior to intercourse. A back up film may also be provided upon participant request or at the discretion of the investigator.
- A directed physical exam will be performed if indicated.
- The participant will be instructed to ask her partner, prior to her next visit, if he has had any AEs involving the urogenital system or whether he has had any serious AEs.
- 6.5.4 Visits 4, 7, 10 (PCT Baseline Cycle, PCT ZB-06 Cycle and post-product-use safety cycle

The participant will return to the clinic 2-3 hours after coitus ends and within 27 hours of the mucus check visit (above, visits 3, 6 and 9).

- The participant will be asked if she has any new or worsening medical problems or symptoms or used any medications since the last study visit. In addition, she will be asked if her partner has had any AEs involving the urogenital system or associated with the use of study products (as applicable) and whether he has had any serious AEs.
- A blood sample (approximately 2 teaspoons) will be obtained at visit 7.
- A wet mount or urine dipstick, or other tests, will be performed if indicated. If the test is positive for candidiasis, BV, or UTI the participant will be treated, preferably with oral medication, and continued in the study.
- Vaginal swabs or aspirate, and endocervical mucus will be obtained.
- The participant will again undergo a pelvic exam during which a sample of cervical and vaginal secretions will be evaluated for midcycle characteristics and the presence of sperm. At visits 4 and 7, a colposcopy exam of the cervix and vagina will be performed to observe if there are signs of irritation of the external genitalia, cervix, and vagina will be noted as observed with naked eye. Baseline PCT results will be interpreted and managed as listed in Appendix B.
- A directed physical exam will be performed if indicated.

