6.5.5 Visits 5 and 8 (24 hours post PCT safety checks)

- The participant will be asked if she has any new or worsening medical problems or symptoms or used any medications since the last study visit. In addition, she will be asked if her partner has had any AEs involving the urogenital system or associated with the use of study products (as applicable) and whether he has had any serious AEs.
- A colposcopy assessment will be performed
- Vaginal swabs or aspirate, endocervical mucus and a cervicovaginal fluid lavage (CVL) will be obtained.
- A blood sample (approximately two teaspoons) will be obtained.
- Urine will be obtained for urinalysis and reflex urine culture.
- Vaginal pH and slide for Nugent score will be obtained at visit 8.
- At the end of Visits 5 and 8, the participant will be given additional condoms if needed and instructed to contact the study coordinator on the first day of her next menses at which time instructions regarding sexual activity and checking urinary LH will be given. The participant will be reminded that from the start of her menses until menstrual cycle day 10, she and her partner should use study provided condoms for each act of intercourse. There should be no intercourse or use of intravaginal products (including spermicide) after menstrual cycle day 10.
- The participant will be provided with a new ovulation prediction kit. When she contacts the clinic on the first day of her next menses, she will be instructed to begin daily urine testing starting on day 10 of her cycle. She will be instructed to contact the study coordinator if a urine test result is positive. Her test cycle mucus check visit will be scheduled for the day of the positive test (preferred) or the next day at the latest. However, if she has not had a positive urine test result by day 22, she will be considered anovulatory and will either be discontinued from the study or allowed to try another cycle, depending on ZabBio, Inc. and investigator discretion.

- A wet mount or urine dipstick, or other tests, will be performed if indicated. If the test is positive for candidiasis, BV, or UTI the participant will be treated, preferably with oral medication, and continued in the study. Note that these vaginal infections may be treated with vaginal medication subsequent to 24 hr check visits.
- At visit 8, the participant will fill out an acceptability questionnaire.

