The secondary endpoint will be the incidence of Grade 2 or greater adverse events in the participant and her male partner in the interval between the baseline intercourse without product (Visit 4) and Visit 6, in comparison to the incidence of Grade 2 or greater adverse events in the interval between intercourse with product use (Visit 7) and Visit 9. Additional related analyses will include the incidence of *total* adverse events in the participant and her male partner in the interval between the baseline intercourse without product (Visit 4) and Visit 6, in comparison to the incidence of *total* adverse events in the participant and her male partner in the interval between the baseline intercourse without product (Visit 4) and Visit 6, in comparison to the incidence *total* adverse events in the interval between intercourse with product use (Visit 7) and Visit 9, as well as comparisons of adverse event severity in the two intervals. For comparison of the two intervals, the Wilcoxon Signed Rank Test will be utilized. An assessment of relatedness to study product will be made for adverse events as supplemental information. Adverse event evaluations will include symptoms, epithelial defects assessed by colposcopy, and laboratory safety blood tests. Emphasis will be placed on adverse events that are urogenital, product-related and/or serious among female and male participants.

7.5.3 Exploratory Endpoints:

Exploratory endpoints will include the following:

- 1. Antisperm antibody concentrations in *vaginal fluid* measured by ELISA at baseline, at 2-3 hours and at 24 hours after intercourse with and without product use and at 1 month after product (ZB-06 film) use.
- 2. Sperm agglutination titer in *vaginal fluid* measured by endpoint dilution at baseline, and at 2-3 hours and at 24 hours after intercourse with and without product used, and at 1 month after product use.
- 3. Concentrations of antisperm antibody in *endocervical mucus* samples measured by ELISA at baseline, and at 2-3 hours and at 24 hours after intercourse with and without product use, and at 1 month after product use.
- 4. Sperm agglutination titer in *endocervical mucus* measured by endpoint dilution at baseline, and at 2-3 hours and at 24 hours after intercourse with and without product use, and at 1 month after product use.

- 5. Concentrations of antisperm antibodies in *serum*, and measured by ELISA at baseline, at 24 hours, and at 1 month after exposure to ZB-06 film.

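### The paired safety comparison in 7.5.2 includes findings from examinations that are not scheduled alike in the no-product and product windows, so the two incidences can differ by schedule alone

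*Combined protocol and SAP*

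**What the plan says.** Section 7.5.2 defines the secondary endpoint as the incidence of Grade 2 or greater adverse events "in the interval between the baseline intercourse without product (Visit 4) and Visit 6", compared with the incidence "in the interval between intercourse with product use (Visit 7) and Visit 9". Total adverse events and severity are compared over the same two windows, and the test is the Wilcoxon signed rank test. On what is counted: "Adverse event evaluations will include symptoms, epithelial defects assessed by colposcopy, and laboratory safety blood tests". Section 8.3 makes laboratory and other abnormal findings adverse events when the investigator judges them clinically significant.

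The schedule is set elsewhere:

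- Blood panels (6.2): "Safety bloods (hematology, and metabolic panel) will be obtained at screening at Visit 8". I read this as screening and Visit 8.
- Colposcopy at mucus-check visits (6.5.3): "At visits 3 and 6, a colposcopy exam of the cervix and vagina will be done". Visit 9 is not named.
- Colposcopy at postcoital visits (6.5.4): "At visits 4 and 7, a colposcopy exam of the cervix and vagina will be performed".
- Colposcopy at the 24-hour visits, 5 and 8 (6.5.5): "A colposcopy assessment will be performed". The colposcopy row of Appendix A likewise stops at Visit 8.
- Urinalysis (6.5.3): "Urine will be obtained for urinalysis and reflex urine culture at visits 3 and 6". Section 6.5.5 adds Visits 5 and 8.
- Male partner: 4.1 has his events asked about at each visit, through the woman or from him, and adds a telephone interview within 72 hours of intercourse with product. The Appendix A footnote on the men's questionnaire says that the call includes questions on adverse events. No matching call is scheduled after the baseline intercourse.

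**The concern.** The no-product window is the within-couple control for the only secondary objective, safety, in a first-in-human study. A paired comparison of incidence is interpretable only if events have the same chance of being detected in both windows. Here some events can be found only by an examination, and the examinations differ between windows. Nothing in 7.5.2 restricts the comparison to matched examinations or allows for their number.

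The blood panel is the clearest case. With no scheduled panel between screening and Visit 8, an abnormality that arose during the no-product cycle would first be seen at Visit 8 and counted in the product window. The exclusion in 8.3 for abnormalities present before treatment gives little protection, because the last scheduled look before product is screening.

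**Working it through.** The plan gives no expected rate or power for the safety endpoint, so there is no stated figure to reproduce; the power statement in 7.2 concerns sperm counts only.

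**Step 1: count scheduled opportunities per woman or couple.**

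| Source | Visits 4-6 | Visits 7-9 | Closing visits (6 and 9) excluded |
|---|---|---|---|
| Adverse-event query at visit | 3 (4, 5, 6) | 3 (7, 8, 9) | 2 vs 2 |
| Safety blood panel | 0 | 1 (8) | 0 vs 1 |
| Colposcopy | 3 (4, 5, 6) | 2 (7, 8) | 2 vs 2 |
| Urinalysis | 2 (5, 6) | 1 (8) | 1 vs 1 |
| Scheduled partner telephone interview | 0 | 1 | 0 vs 1 |

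The panel and partner-interview imbalances do not depend on the window edge. The colposcopy and urinalysis imbalances do.

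The CBC row of Appendix A is unclear in the extracted text, so I rely on 6.2. The marks that appear to sit on that row (Visits 3, 6 and 8) match the visits at which 6.5.3 and 6.5.5 place vaginal pH, and 6.5.3 schedules no blood draw at Visit 3. If the row did include Visit 6, panels would be 1 vs 1 with closing visits counted, although the Visit 6 sample would precede product.

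**Step 2: incidence with no film effect.** The documents give no rates. Assume a chance p of a new countable finding at each colposcopy and q at each panel, all independent:

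- No-product, closing visits counted: A = 1 − (1−p)³
- No-product, closing visits excluded: A′ = 1 − (1−p)²
- Product, either way: B = 1 − (1−p)²(1−q)

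Hence B − A = (1−p)²(q − p), and B − A′ = (1−p)²q.

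| Assumed p, q | A vs B | A′ vs B |
|---|---|---|
| 2%, 5% | 5.9% vs 8.8% | 4.0% vs 8.8% |
| 2%, 10% | 5.9% vs 13.6% | 4.0% vs 13.6% |
| 5%, 0% | 14.3% vs 9.8% | 9.8% vs 9.8% |
| 2%, 2% | 5.9% vs 5.9% | 4.0% vs 5.9% |

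For the first row: 1 − 0.98³ = 0.0588; 1 − 0.98² × 0.95 = 0.0876; 1 − 0.98² = 0.0396. Among 15 women that is 0.9 vs 1.3 expected (0.6 vs 1.3 with closing visits excluded). With closing visits counted, the sign of the artefact is the sign of q − p, and it vanishes at p = q. With them excluded, it is never below zero.

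The model leaves out urinalysis and the partner interview. It also treats colposcopies about a day apart as independent, which overstates what repeated looks add.

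**Step 3: effect on the test.** With one event indicator per couple, an exact two-sided p below 0.05 needs at least six discordant couples all in one direction: 2 × 0.5⁵ = 0.0625, 2 × 0.5⁶ = 0.031. (The 0.05 level appears in 7.5.3 only, and sidedness is not stated.) Simulated rejection rates with no film effect and closing visits counted, using the exact sign test as a stand-in for the planned test with 15 couples, were 0.4% (p = 5%, q = 0), 2.1% (p = 10%, q = 0), 0.5% (p = 2%, q = 10%) and 4.1% (p = 5%, q = 20%).

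**Step 4: after matching.** Colposcopy at Visits 4+5 vs 7+8 and no panel in the comparison give equal counts, so the expected difference is 0 for any p and q.

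**The case against.** Several points on the other side have force.

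- The endpoint is Grade 2 or greater, and 8.3 admits only clinically significant findings. Section 9.1.1 places grade 2 erythema or edema at more than half the surface and makes one such case a criterion for pausing enrollment. Qualifying findings should therefore be rare. This stands: rates of 5-10% per examination suit the total-event analysis better than the Grade 2+ endpoint. At 1% for both, the incidences are 3.0% vs 3.0% with closing visits counted and 2.0% vs 3.0% without.
- The colposcopy and urinalysis imbalances follow from one reading of an undefined boundary. This stands. Urinalysis is also not named in the 7.5.2 sentence and enters only through the general rule in 8.3. A pelvic examination is still done at Visit 9, so visible lesions would not go wholly unseen.
- Sections 6.2 and 7.5.2 put the emphasis on events that are urogenital, product-related or serious, and the plan has other comparators: screening bloods, colposcopy at Visit 6 before product, and immune mediators with and without film. This softens the consequence, but the unmatched sources remain in the stated comparison.
- The study is small and exploratory, with no power claim for safety. This stands too.

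A reader might go further and infer that the incidences must differ, or that the schedule is tilted one way, against the film or towards hiding harm. The documents support neither. The blood panel and partner interview raise detection on the product side. The extra colposcopy and urinalysis, if counted, raise it on the no-product side and could mask a film effect. The documents give no rates from which to net these.

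**Conclusion.** The concern holds in a limited form: ascertainment is unequal, so the two incidences can differ with no film effect. The part that depends on no window boundary is the blood panel, 0 vs 1, and the scheduled partner interview, 0 vs 1. Colposcopy at 3 vs 2 and urinalysis at 2 vs 1 apply only if closing-visit examinations count.

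Net direction is unknown, and any size rests on assumed rates; 5.9% vs 8.8% (or 4.0% vs 8.8%) is an illustration at 2% per colposcopy and 5% per panel, not an estimate. It would be wrong to infer that the schedule makes a falsely significant result likely: the simulated rates stayed at or below about 4%. The effect is mainly on the reported incidences, which are the main safety description in a first-in-human study of this size. Because it can be removed by wording alone, it should be changed.

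**What to change.** In 7.5.2:

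1. Limit the paired comparison to sources scheduled alike in both cycles: adverse events from the same visit queries, colposcopy at Visits 4+5 vs 7+8, and urinalysis at Visit 5 vs 8.
2. Treat Visit 6 examination and urine findings as the pre-product baseline of the product cycle, not as no-product events. This also settles the boundary for those examinations.
3. Report Visit 8 blood-test findings separately, against screening.
4. Report separately the adverse events elicited only by the direct male-partner interview. Without this step the visit queries would be matched but partner events would not.

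The cost is analysis wording only; no visit, sample or procedure changes. The small downside is that findings first seen at Visit 6, and those from the unmatched sources, leave the compared count. They are still reported.

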8 ADVERSE EVENTS AND SERIOUS ADVERSE EVENTS

The investigator is responsible for the detection and documentation of events meeting the definition of an AE or serious adverse event (SAE) as provided in this protocol. AE event monitoring for this study will begin at the time of informed consent (Visit 1) through the last visit or follow up phone call. In order to fulfill safety reporting obligations, the investigator should promptly report any SAEs resulting from study participation.

8.1 Definition of an AE

An AE is any untoward medical occurrence in a clinical investigation subject administered a pharmaceutical product, regardless of the suspected causal relationship with the study treatment. An AE can therefore be any unfavorable and unintended sign (including a clinically significant abnormal laboratory finding), symptom or disease temporally associated with the use of a medicinal product, whether or not considered related to the use of the medicinal product.

The definition of an AE includes:

- An exacerbation of a pre-existing illness
- An increase in the frequency or intensity of a pre-existing episodic event or condition
- Any condition detected or diagnosed after the start of study treatment even though the condition may have been present prior to the start of the study
- A continuous persistent disease or symptom present at baseline that worsens after the start of the study

The definition of an AE does not include:

- A medical or surgical procedure such as surgery, endoscopy, tooth extraction, or transfusion (although the condition that leads to the procedure may be an AE)
- A pre-existing disease or condition present at the start of the study that does not worsen during the study
- Any situation where an untoward medical occurrence has not occurred (for example, hospitalizations for cosmetic elective surgery or social admissions)
- An overdose of either the study drug or a concurrent medication without any resulting signs or symptoms

AEs may also include post-treatment events that occur as a result of protocol-mandated procedures (e.g., invasive procedures or modification of a subject's previous therapeutic regimen).

8.2 Definition of an SAE

A serious adverse event (SAE) is an AE which meets any of the following criteria:

```
Version No.: 4.0
```

- Results in death
- Is life-threatening
- Requires hospitalization or the prolongation of existing hospitalization
- Results in a persistent or significant disability or incapacity
- Is a congenital anomaly or birth defect

In addition, important medical events that may not result in death, be life-threatening, or require hospitalization may be considered serious when, based on appropriate medical judgment, the investigator determines that the event may jeopardize the subject and may require medical or surgical intervention to prevent one of the outcomes listed in this definition. Examples of such medical events include allergic bronchospasm requiring intensive treatment in an emergency room or at home, blood dyscrasias, or convulsions that do not result in hospitalization, or the development of drug dependency or drug abuse.

Hospitalization for elective treatment of a pre-existing condition that did not worsen during the study is not considered an AE. Any complications that occur during hospitalization are AEs. If a complication prolongs hospitalization, then the complicating event is an SAE.

Life-threatening means that the subject was, in the view of the investigator, at immediate risk of death from the event as it occurred. It does not mean that the event, had it occurred in a more severe form, might have caused death.

8.3 Clinical Laboratory Abnormalities and Other Abnormal Assessments

Abnormal laboratory findings or other abnormal assessments (e.g., ECGs, vital signs) that are judged by the investigator as clinically significant should be recorded as AEs. Clinically significant abnormal laboratory findings or other abnormal assessments that are detected after the start of study treatment, or that are present before the start of study treatment and worsen after study treatment, are considered AEs.

Clinically significant abnormal laboratory findings or other abnormal assessments that are associated with a disease (unless judged by the investigator as more severe than expected for the subject's condition) or that are present before the start of study treatment and do not worsen after study treatment are not included as AEs.

The investigator should exercise his or her medical and scientific judgment in deciding whether an abnormal laboratory finding or other abnormal assessment is clinically significant.

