5.5 Study Drug Accountability Procedures

The ZB-06 film will be stored in a temperature-monitored, access-controlled refrigerator at 2-8 $^{\circ}$ C until dispensed by the study staff to the participant at the product cycle cervical mucus check (CMC) visit (Visit 6). A log of receipt and dispensing will be kept by the study staff. Unused films will be returned to the Sponsor after study completion.

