8.4 Method, Frequency, and Time Period for Detecting AEs and SAEs

Each subject will be monitored for AEs from the time of informed consent (Visit 1) through their last visit or follow up phone call. All AEs and SAEs, regardless of attribution (i.e., relationship to study drug), will be collected during this time period. The collection period

will end when the subject completes the Follow-Up phone call unless there is an ongoing AE which requires monitoring beyond this time point.

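### Section 8.3's rule for abnormal findings, read literally, would drop new colposcopic and urinalysis findings from the no-product window of the secondary comparison but keep them after the film; it conflicts with 7.5.2 and 8.4

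*Combined protocol and SAP*

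**What the plan says.** Section 7.5.2 of the combined protocol and SAP compares Grade 2 or greater adverse events in participant and partner across two windows. The no-product window is worded thus: "in the interval between the baseline intercourse without product (Visit 4) and Visit 6, in comparison to the incidence of Grade 2 or greater adverse". The product window runs from Visit 7 to Visit 9. The section adds the same comparison for total adverse events and for severity, all by the Wilcoxon signed rank test. On content it states: "Adverse event evaluations will include symptoms, epithelial defects assessed by colposcopy, and laboratory safety blood tests".

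Section 8.3 decides when an abnormal laboratory result or other assessment is an adverse event, and it says three things:

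- The opening sentence has no time limit: abnormal assessments "that are judged by the investigator as clinically significant should be recorded as AEs".
- The next sentence counts clinically significant findings "that are detected after the start of study treatment, or that are present before the start of study treatment and worsen after study treatment".
- The exclusion then says findings "that are present before the start of study treatment and do not worsen after study treatment are not included as AEs".

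Section 8.4 sets the collection period: "Each subject will be monitored for AEs from the time of informed consent (Visit 1) through their last visit or follow up phone call". It continues: "All AEs and SAEs, regardless of attribution (i.e., relationship to study drug), will be collected during this time period".

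Study treatment is one film, kept in storage "until dispensed by the study staff to the participant at the product cycle cervical mucus check (CMC) visit (Visit 6") and inserted about half an hour before intercourse in the product cycle (5.4).

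**The concern.** The second and third statements of 8.3 are tied to the start of study treatment. That suits a safety listing whose purpose is to show what appeared after dosing. It does not suit a within-woman comparison whose control period lies before dosing. If site staff apply 8.3 as worded, a class of findings can be counted in the product window but not in the control window, and the film looks worse even if it does nothing.

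If they follow the opening sentence of 8.3 instead, the findings are counted in both windows. Two staff members could therefore classify the same Visit 5 colposcopic finding differently, each with text to support the choice. Under 4.3 the investigator, who makes the clinical-significance judgement, is not blinded to the cycle.

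**Working it through.** The plan gives no figure for this point, so there is none to reproduce. The check sets the text against the visit schedule and then illustrates the size.

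**1. Position of treatment.** The film is dispensed at Visit 6 (5.5) and used before Visit 7 (5.4). The window from Visit 4 to Visit 6 therefore lies wholly before treatment, and the window from Visit 7 to Visit 9 wholly after it.

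**2. A new finding at Visit 4 or 5.** Suppose it is clinically significant, has no diagnosis or symptoms, and does not worsen after the film. It was not detected after treatment started and did not worsen after treatment, so it meets neither condition of the second statement. It was present before treatment and did not worsen, so on its face it meets the exclusion. Only the opening sentence would count it.

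**3. The same finding, new at Visit 7 or 8.** It was detected after treatment started, so it counts.

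The asymmetry concerns findings new in each window. A finding that persists unchanged from the no-product window is not counted after the film either.

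**4. Which examinations are affected** (Appendix A, with 6.2 for bloods):

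| Assessment | No-product window | Product window | Affected by 8.3? |
|---|---|---|---|
| Colposcopy | Visits 4, 5, 6 | Visits 7, 8 | Yes |
| Urinalysis | Visits 5, 6 | Visit 8 | Yes |
| Blood count, metabolic panel | none | Visit 8 | No; there is nothing to exclude |

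Colposcopy and urinalysis are also done at Visit 3, before baseline intercourse. Blood count and metabolic panel are otherwise drawn only at screening.

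**5. Size, by illustration.** n = 15 (7.2). The rate p of a new clinically significant finding per cycle is an assumption, because the documents give none. It is taken as equal and independent in the two windows.

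Expected women with a finding:
- literal rule: 0 versus n × p
- common rule: n × p versus n × p

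At p = 10% this is 15 × 0.10 = 1.5. At p = 20% it is 15 × 0.20 = 3.

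For the test, take each woman as yes or no in each window. All non-zero differences then have the same size, so an exact signed rank test reduces to a sign test. With k women positive in the product window only and none in the other, the two-sided p-value is 2 × 0.5^k. For k = 5 it is 0.0625 and for k = 6 it is 0.031, so six are needed at two-sided 0.05 (an assumed level, since 7.5.2 does not state its own). Under the literal rule the chance of a false signal is P(X ≥ 6) with X ~ Binomial(15, p). Under the common rule it is the chance that an exact McNemar test is significant in either direction.

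| Assumed p | Expected, literal rule | Expected, common rule | False signal, literal | False signal, common |
|---|---|---|---|---|
| 5% | 0 vs 0.75 | 0.75 vs 0.75 | 0.01% | 0.01% |
| 10% | 0 vs 1.5 | 1.5 vs 1.5 | 0.2% | 0.1% |
| 20% | 0 vs 3 | 3 vs 3 | 6.1% | 0.8% |
| 30% | 0 vs 4.5 | 4.5 vs 4.5 | 27.8% | 1.4% |

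At 10% or below the harm is a distorted description. A false test result becomes a practical risk only from about 20% upwards.

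**The case against.** The strongest reply is that nobody need read 8.3 this way. Its opening sentence has no time limit, 8.4 collects all adverse events from consent, Appendix A marks adverse-event collection at every visit, and 8.1 ties its own pre-existing-condition rule to the start of the study. Section 7.5.2 is the specific text and plainly expects events, colposcopic ones included, before treatment. The exclusion can also be read as aimed at abnormalities carried into treatment, not at a Visit 4 finding that has resolved. Section 8.3 does not mention colposcopy; its examples are ECGs and vital signs.

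Most of this stands as evidence that the documents disagree, and it rules out treating the exclusion as certain. It does not remove the conflict. Section 8.4 says when adverse events are collected, not what qualifies as one. Within 8.3 the exclusion is the more specific statement. Section 8.1 describes an adverse event as occurring in a subject who has been given a product, which also sits badly with a pre-treatment window. Applying 8.3 to colposcopy is an inference, but a reasonable one given what 7.5.2 includes.

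Three stronger readings are tempting, and the documents do not support them:

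- **That objective findings can enter only the product window.** Under 8.5 a diagnosis, or failing that signs and symptoms, is recorded in preference to the bare abnormal finding where possible. Symptoms and diagnosed conditions, such as a urinary infection, can therefore enter either window.
- **That 8.3 also causes an imbalance in laboratory bloods.** That imbalance comes from the schedule, because no safety blood is drawn between Visits 4 and 6.
- **That the comparison is biased against the film by definition.** The bias arises only if the exclusion is applied. If both windows were counted alike, the no-product window would hold one more colposcopy (Visit 6, with none at Visit 9), an imbalance in the other direction.

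**Conclusion.** The point holds as a conflict within the plan with a conditional bias. Applied literally, 8.3 would remove new, non-worsening, clinically significant colposcopic or urinalysis findings without diagnosis or symptoms from the control window, and keep them in the product window. For those findings the comparison would be biased against the film. Whether this happens depends on which sentence the site follows, and the documents do not settle that.

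The size is unknown. The figure of 0 versus 1.5 to 3 findings in 15 women rests on the literal reading and an assumed equal rate of 10 to 20%. That rate is for clinically significant findings of any grade. At Grade 2 or greater the numbers should be smaller: 9.1.1 places erythema or edema at grade 2 only when it exceeds half the surface, and makes a single such case a criterion for pausing enrollment. The effect would show mainly in the total-event and severity comparisons that 7.5.2 adds. In an exploratory 15-couple study, severity is minor to moderate.

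**What to change.** State in 7.5.2 and 8.3 that, for the two-window comparison, a clinically significant colposcopic or urinalysis finding counts if it is new or worse than at the pre-coital examination of the same cycle, whether or not treatment has started. The reference is Visit 3 for the no-product window and Visit 6 for the product window.

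With that:

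- Restrict the paired comparison of such findings to examinations made in both windows: colposcopy at Visits 4 and 5 against Visits 7 and 8, and urinalysis at Visit 5 against Visit 8.
- Report the Visit 8 safety bloods descriptively against screening, outside the paired comparison. No blood is drawn at Visit 3 or Visit 6, so the same-cycle reference cannot be applied to them.
- Reconcile the wording of 8.1 and 8.3 with 8.4, so that an event before first product use can qualify as an adverse event.

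The cost is a few sentences, best agreed before findings are classified. No procedure is added, because colposcopy and urinalysis are already scheduled at Visits 3 and 6. The downside is that slightly fewer findings enter the paired comparison: those first seen at Visit 6, and the blood results.
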